CSP #591, version 11.0, February 16, 2018 25 Participants meeting eligibility criteria will then be assigned to treatment. As indicated in **Section VI.A**, the Site Coordinator will use the system established by the Palo Alto CSPCC to obtain the participant's treatment assignment. The Site Coordinator will contact the participant by phone to provide information about the participant's treatment assignment and schedule the participant's initial therapy appointment. If more than 30 days elapses between the Phase 3 appointment and the first treatment session, the CAPS will be re-administered to allow for an accurate baseline measurement. The SC will attempt to contact the participant by phone 5 times and finally with a letter requesting a response of interest in the study. If there is stil no response it will be assumed that the potential participant is no longer interested in the study.

V. TREATMENT

A. Prolonged Exposure

Prolonged Exposure ([name] et al., 2007) is a manualized, 90-minute, 8-15 week treatment program based on emotional processing theory ([name] & Kozak, 1986; [name] & Cahill, 2001), which posits that anxiety disorders, including PTSD, reflect pathological fear structures in which emotional and cognitive associations among different elements do not accurately represent reality and renders the individual dysfunctional and distressed. PE is designed to correct erroneous connections in the targeted memory structure. PTSD sufferers typically experience two key pathological emotional response sets and related cognitions: "The world is an utterly dangerous place," and "I am completely incompetent and unable to cope with stress." In this study, the 12-session protocol will be followed, but participants who improve more rapidly may finish in 10 sessions and those who improve more slowly may have up to 2 additional sessions to continue working on exposure. The procedure for determining number of sessions is described in **Section VIII.B.3**.

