Sessions 7-12: After reviewing the problematic thinking patterns, the final worksheet and first of five themes is introduced. The Challenging Beliefs Worksheet compiles the content of all the previous worksheets and adds a final column in which the patient generates a more balanced and fact-based statement. The patient is asked to rate how much he or she believes this new statement and how much they now believe the old stuck point. The patient is also asked to name and rate the intensity of emotions before and after completing the worksheet. One theme is explored each week in addition to the person's individual stuck points. Each of the themes, safety, trust, power/control, esteem and intimacy can be self or other oriented. Three other assignments are given in the last few sessions in addition to reading handouts on the themes and completing worksheets. Patients are asked to practice giving and receiving compliments to reengage with other people and to challenge their core beliefs and are asked to do at least one pleasurable or worthwhile activity for themselves each day. This latter assignment is to help the patient reestablish what they used to enjoy doing and to build self-worth. Either of these assignments may trigger stuck points that can then be challenged. Behavioral activation can serve as relapse prevention for depression as well. The final assignment before session 12 is to rewrite the impact statement about how the patient now thinks about the causes of the trauma.

Session 12 begins with a review of the intimacy work sheets and then the patient reads the new impact statement. The therapist reads the original statement and they compare the differences. They also notice areas that the patient needs to continue to practice working on stuck points and review the whole course of therapy.

VI. TREATMENT ASSIGNMENT

A. Randomization

After the Site Coordinator has gone through the checklist to verify that the participant has signed the informed consent form, met all the enrollment criteria, and completed the baseline assessments, he/she can use the system established by the Palo Alto CSPCC to randomize the participant. Participants will be randomly assigned in a 1:1 ratio to receiving PE or CPT. Participant randomization will be based on permuted blocks within each study center. After the participant is randomized, the Site Coordinator will obtain the treatment assignment and complete the case report form (CRF) on randomization.

B. Blinding

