Screening/baseline/interview	30/20/50
Mid-treatment	50
Posttreatment	75
3-month follow-up	85
6-month follow-up	100

B. Treatment

1. Assignment

Participants will be randomly assigned to treatment following the completion of baseline assessment measures that establish their eligibility for the trial.

2. Delivery

Both study treatments, which are summarized in **Section V**, will be delivered according to standardized manuals. We will use the manuals and the therapist and patient materials developed for the PE and CPT rollouts to administer the treatments. The manual for each treatment is provided in Volume 2 of the study protocol. Treatment will be delivered in an outpatient setting.

PE and CPT will be administered approximately weekly, although sessions may be held more or less frequently than once a week if needed, e.g., to accommodate a patient's scheduling needs or to help a patient finish treatment within 20 weeks. For the sake of brevity, session frequency is described as "weekly" throughout this protocol. The standard protocol for PE is 8-15 sessions (10 sessions were used for PE in CSP #494), whereas the standard protocol for CPT is 12. Given the flexibility in the number of sessions allowed according to the protocols in the VA rollouts, it would be difficult to constrain the total number of sessions to 12 in CPT and 10 in PE. Therefore, we propose to administer 12 sessions of each treatment as a standard "dose" but to allow participants who improve more rapidly to finish in 10 or 11 sessions and participants who have not attained adequate improvement by session 12 to have up to 2 additional sessions.

Data from the rollouts suggests that this range will address the needs of most Veterans who participate in the trial (**Table VIII.3**). The average number of sessions among treatment completers is 11-12. There are not fixed criteria for determining completion in either rollout, however. In PE, completion is defined as attending at least 8 sessions. In CPT, completion is

based on improvement as determined by clinical judgment and decrease in PCL scores, which is more comparable to what we propose to use.

	Ν	Mean (SD)	< 10	10-14	> 14	
Prolonged Exposure	1,723	11.09 (2.62)	28.9%	59.7%	11.4%	
Cognitive Processing Therapy	689	11.83 (1.88)	8.1%	87.0%	4.9%	

Table VIII.3. Number of Sessions in Veterans Completing Treatment in the VA Rollouts

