Although our sample size calculation is based on DSM-IV CAPS total score data observed in the CSP#494, the effect size of 0.25 is independent of DSM versions. In addition, a correlation coefficient among participants treated by the same therapist is a robust statistics for both location and scale change of CAPS total scores. We expect a negligible difference in inflation factors between DSM versions. Therefore, the sample size derived below is appropriate for CAPS on DSM-5.

B. Sample Size and Power Considerations

1. Planned primary analysis for the primary outcome

Linear mixed effects models (SAS PROC MIXED) will be used to compare the primary outcome between the two treatment groups. The mixed effects model will include time, treatment, treatment by time interaction and site as fixed effects, and participant and therapist as random effects. Specifically let Y_{ijk} denote the CAPS total score measured at timepoint *k* for the *j*th participant treated by therapist *i*. The mixed effects model for the primary analysis is:

$$Y_{ijk} = \alpha + \beta_k + \gamma_{z(i)} + (\beta\gamma)_{kz(i)} + \theta^T w_{ij} + u_i \mathbb{1}_{\{k \neq 0\}} + b_{ij} + \varepsilon_{ijk}$$

where i = 1, ..., I, $j = 1, ..., J_i$, k = 0, 1, 2, 3 with k = 0 indicating baseline and k = 1, 2, 3 indicating the three post-treatment timepoints, z(i) is the treatment that participant j treated by therapist iis randomized to, β_k is the time effect (fixed), $\gamma_{z(i)}$ is the treatment effect (fixed), $(\beta\gamma)_{kz(i)}$ is the time by treatment interaction (fixed), w_{ij} denotes the vector of other covariates in the model (such as site or key baseline characteristics) and θ is the associated regression parameter, u_i is the random therapist effect for therapist i, $1_{\{k \neq 0\}}$ is the indicator for k not equal to zero, b_{ij} is the random participant effect for participant j treated by therapist i, ε_{ijk} is the random error at the k^{th} timepoint for participant j treated by therapist i. While other covariance structures will be used to assess their impact on study results, for simplicity and ease of interpretation we assume in the primary analysis that u_i , b_{ij} and ε_{ijk} are independent and have the following distributions:

$$u_i \sim N(0, \sigma_P^2), b_{ij} \sim N(0, \sigma_{BS}^2), \varepsilon_{ijk}, \sim N(0, \sigma_{WS}^2)$$

Under this mixed effects model, the variance of CAPS total score at timepoint k is

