Changes to the original statistical plan for analyzing study data will follow the CSP standard operating procedures for amending the study protocol, which require review and approval by the CSPCC Director and several oversight groups including the Executive Committee and the DMC. As needed, updates may also be required to other study documents such as the Case Report Forms and Operations Manual.
XI. MONITORING AND REPORTING ADVERSE EVENTS

A. Importance of Adverse Event Reporting

Timely and complete reporting of safety information assists study management in identifying any untoward medical occurrence, thereby allowing: a) protection of safety of study participants, b) a greater understanding of the overall safety profile of the study treatments and therapeutic modalities, c) improvements in study design or procedures, and d) compliance with regulatory requirements.

B. Role of the Local Site Investigator in Adverse Event Monitoring

The LSI will be responsible for the adverse event reporting requirements as outlined below:

- Reviewing the accuracy and completeness of all adverse events (AE) reported.
- Compliance with VA CIRB policies for reporting AEs and/or serious adverse events (SAEs).

[* Note: In June 2015, the VA published an update to "Reporting of Adverse Events in Research to the Office of Research Oversight (ORO)" in VHA Handbook 1058.1. Investigators should be aware of these reporting requirements. This, however, does not eliminate the need for investigators to report both adverse events and serious adverse events to the CSP #591 Sponsor as per the study protocol.]

• Closely monitoring research participants at each study visit for any new SAEs.

C. Collection of Safety Information

1. Adverse Events

Adverse events (AEs) are defined by the International Conference on Harmonization (ICH) for Clinical Safety Data Management (ICH-E2A) as "any untoward medical occurrence in a clinical investigation subject that is subjected to one of the study treatments that does not necessarily have to have a causal relationship with the treatments. An AE, therefore, can be any unfavorable or unintended sign (including an abnormal laboratory finding), symptom, or disease temporally associated with the study interventions." For the purposes of CSP #591, the study treatments are a) the Prolonged Exposure (PE) treatment and related activities and b) the Cognitive Processing Therapy (CPT) treatment and related activities.

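### Does a repeat CAPS before session 1 leave the baseline of the primary outcome undefined?

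*Protocol*

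**What the plan says.** Protocol IV.C.3 (Phase 3) sets the trigger: "If more than 30 days elapses between the Phase 3 appointment and the first treatment session, the CAPS will be re-administered". The same sentence gives the purpose; the CAPS is "re-administered to allow for an accurate baseline measurement". Just before it, the section says "The Site Coordinator will contact the participant by phone to provide information about the" treatment assignment and books the first session. The Appendix E log dates this text to version 9.0, August 2017.

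Two other sections place baseline before randomisation. Under VI.A, once the Site Coordinator has verified that the participant has, among other things, "completed the baseline assessments, he/she can use the system established by the Palo Alto CSPCC to randomize the participant". VIII.B.1 says: "Participants will be randomly assigned to treatment following the completion of baseline assessment measures that establish their eligibility for the trial".

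The analysis sections allow one baseline record. The model in X.B.1 is indexed "with k = 0 indicating baseline and k = 1, 2, 3 indicating the three post-treatment timepoints". Protocol X.D.2 and SAP II.H.2 describe baseline only as pre-treatment, which fits both scores. SAP II.K treats several visits in one window as a situation that will not arise, and gives a rule only for late follow-up visits. The SAP (version 1.1, April 2014) is older than the repeat-CAPS text.

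**The concern.** A participant with a delayed start can have two pre-treatment scores, and no analysis section names the one that enters as k = 0. The repeat will normally be taken after randomisation, when the participant already knows the arm. The X.B.1 model has a free treatment term at baseline. If the repeat is used, an arm difference in who is repeated, or in how scores move after assignment, therefore passes straight into the primary contrast.

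A second worry needs no arm difference. Two defensible baselines give two primary estimates. SAP II.D.2 has the coordinating centre run arm comparisons for each Data Monitoring Committee report, so in principle the choice could be made with results in view.

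**Working it through.** **The plan's own figure.** Inputs from Protocol X.B.2 and X.B.3: therapist variance 36, within-subject variance 174, three follow-up scores, 8 participants per therapist.
- τ² = 36 + 174/3 + 174 = 268, so τ = 16.4.
- ρ = 36/268 = 0.134 and f = 1 + 7 × 0.134 = 1.94.
- 226 per group × 1.94, rounded up, is 439 per group, or 878 in total, as stated.

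Either single baseline score contributes one term of 174 to τ². The choice therefore changes neither the sample size nor the power (90.8% at 900 with complete follow-up).

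**Can it happen within the windows?** SAP II.J allows 0–7 days from Phase 3 to randomisation and 0–30 days from randomisation to session 1. The longest in-window gap is 7 + 30 = 37 days, so yes. The 30-day mark falls at least 30 − 7 = 23 days after randomisation. That the repeat follows randomisation is inferred from these windows and the order of the text; no section states it.

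**How often?** Assuming uniform timing within the windows, the share with a gap above 30 days is (7 × 7/2)/(7 × 30) = 24.5/210 = 11.7%, or 28/248 = 11.3% in whole days. The documents give no count.

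**Bias from a different share repeated in each arm.**
- SE of the contrast = √(2 × 268 × 1.94/450) = 1.52.
- Entry requires the equivalent of a DSM-IV CAPS score of at least 45, so a re-test should drift down. SD = √678 = 26.0 and reliability = 504/678 = 0.743, so the drop is 0.257 × (mean of those selected − mean of all screened).
- In CSP #494, 320 were screened and 284 randomised (IV.C.1), leaving 36; reasons are not given. If all 36 failed on CAPS: 0.257 × (82.2 − 76.6) = 1.44 points. If 18 did: 0.257 × (89.4 − 86.3) = 0.80 points.
- Bias = gap in share × drop:

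| Assumed gap between arms | Bias (points) | Bias/SE | Two-sided error |
|---|---|---|---|
| 5 percentage points | 0.04–0.07 | 0.03–0.05 | 5.01–5.03% |
| 10 percentage points | 0.08–0.14 | 0.05–0.09 | 5.03–5.10% |
| 20 percentage points | 0.16–0.29 | 0.11–0.19 | 5.13–5.41% |

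**Bias from a different shift in each arm.** If a share p is repeated and the arms differ by d points in their shift after assignment, the bias is p × d. With p = 10% and d = 2 this is 0.2 points; if it acts against a true 5-point difference, power is 88.4%. With p = 20% and d = 2 it is 0.4 points and power is 85.7%. Both p and d are assumed.

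**Two estimates with no arm difference.** Swapping the baseline for a share p changes the contrast with variance 2 × p × (2 × 174)/450. At p = 0.113–0.117 the SD is 0.42 points (0.28 SE), and the two estimates correlate 1 − 0.42²/(2 × 1.52²) = 0.96. Under the null, the chance that at least one of the two tests rejects is 6.3%. It is 5.5–5.7% if only 2–3% are repeated and 6.7% if 20% are. These figures apply only if someone picks the baseline after seeing both results.

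**The case for a change.** The strongest case for a change is that the texts pull in different directions. VI.A and VIII.B.1 put baseline before randomisation, IV.C.3 points to a later score, and no analysis section decides. The Phase 3 score precedes randomisation and exists for every randomised participant, which suits an intention-to-treat analysis. Naming it would need no new data. For one person the two scores differ with SD √(2 × 174) = 18.7 points, so the choice is not trivial at individual level. A harsh scenario can also be built: 40% repeated with a 5-point arm difference in shift gives a 2-point bias and cuts power to 50.5%.

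What stands is narrow: the analysis sections do not carry IV.C.3 through, and SAP II.K does not cover the case. The rest is weaker.

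- The plan is not silent. The purpose clause in IV.C.3 points to the repeat as baseline. Requiring the Phase 3 score would reverse that stated purpose and would mean rewriting IV.C.3, so it is more than a clarification.
- A score taken close to the start of treatment has merit of its own: it measures change from the state in which treatment began. Reasonable statisticians differ on this.
- The harsh scenario needs more than three times the in-window share of repeats, and a shift difference as large as the effect the trial is powered to detect. Nothing in the documents suggests either.
- Assignment uses permuted blocks within each centre ("Participant randomization will be based on permuted blocks within each study center"), each site has at least four therapists per treatment, and assessors are central and blinded. A large arm difference in delay or scoring is unlikely, although blinding does not remove a participant's own reaction to the assignment.
- A results-driven switch of baseline faces existing controls. Under X.G, "Changes to the original statistical plan for analyzing study data will follow the CSP standard operating procedures for amending the study protocol", with approval from the coordinating centre's director and oversight groups. XV.A withholds outcome data from participating investigators and the Study Chairman until data collection ends.

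**Conclusion.** No change to the plan is needed. This is a missing detail that analysts can fill sensibly, together with a fair trade-off between a score protected by randomisation and a fresher one. The primary result is sound with either.

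Sample size, τ and power are the same for both scores. Bias is zero unless the arms differ in the share repeated or in the shift, and the documents show no such difference. A 10 to 20 percentage-point gap in repeats, large against an average of 11–12%, would move the estimate by 0.08–0.29 points, or 1.6–5.8% of the 5-point target. A modest difference in shift gives a bias of similar order.

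These sizes rest on uniform timing within the SAP windows, on variances from CSP #494, and on an assumed number of CAPS failures in that trial. Starts outside the windows could raise the share repeated. If the practice began only with the August 2017 text, the share across all 900 could be well below 11–12%; the log does not settle when it began. The 6.3% figure is the cost of choosing the baseline on results, which the plan's controls restrict. It is not an error rate of the plan as written.

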The diagnostic assessments done at study entry will provide final determination of a participant's eligibility for the study by confirming the inclusion and exclusion psychiatric diagnoses. We propose to use screening and consent processes the study team has employed successfully in CSP #420 and CSP #494. All participants, including self-referrals, will enter the study through referral by a mental health clinician or other qualified clinician at the participating site. Participants who are not currently receiving treatment at the site will first undergo an intake at the site's mental health program so that a clinician there can refer them. This strategy helps provide continuity of care for potential participants who do not enter the study, or who terminate from treatment early or need additional treatment during the study.

Screening information will be obtained in three phases, structured so as to minimize both participant burden and cost to the study due to extensive assessment of ineligible participants.

1. Phase 1

In the first phase of screening, the Site Coordinator will consult the referring clinician in order to establish a provisional PTSD diagnosis and other inclusion and exclusion criteria. In CSP #420 and CSP #494 this strategy resulted in a highly efficient screening process. For example, in CSP #494, 43 of the 396 patients who were discussed with a referral source were ruled out at this phase. Of the 353 patients who met with study staff, 320 were screened and 284 were randomized—71.7% of those discussed and 88.8% of those screened.

The referral clinician also would be asked to agree at this time to not treat the participant for PTSD while the participant is receiving study treatment, and would be reminded that treatment for other problems and brief check-ins are possible. The Site Coordinator will then schedule potential participants who are eligible based on the information provided by the referral source for Phase 2 screening. The SC will contact the potential participants initially by phone (up to 5 times) and then by mail with a letter.

2. Phase 2

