The Assessors will introduce the telephone interview portion of the study to the participant informing the participant about the content of the interview and then reminding them that the interview is being recorded. We will digitally record telephone assessments for the purposes of checking interviewer reliability, following procedures used in CSP #566.

All computers used for audio recordings will be VA-issued. Desktop computers will be networked within the VA system and password-protected. Laptops will be VA-issued, encrypted, password protected, and have VPN capabilities. Recorded files for CSP #591 will be saved directly to a secured drive behind the VA firewall. As an additional security measure, recorded files will be password protected.

3. Procedures to Enhance Completion of Assessment Protocols

A number of procedures will be used to minimize the likelihood that participants will fail to complete the schedule of assessments. Detailed contact information will be obtained at study entry to facilitate follow-up, even for participants who move. This information will be updated at subsequent assessments. During treatment, the PCL and PHQ-9 questionnaires will be administered prior to a treatment session. Interview assessments that include the primary outcome will be conducted in telephone appointments scheduled for this purpose. Scheduling will occur by phone when possible. Participants who do not have telephones will be contacted by mail and asked to call the Site Coordinator to make an appointment to come in to the VA Medical Center for the telephone interview or to make arrangements to use a phone elsewhere. Five contact attempts including a final letter will be made before a participant is considered to be

unreachable at that time point. Participants who fail to participate in a scheduled assessment will be contacted by phone (or mail, when necessary) for rescheduling. After two missed appointments without explanation, a participant will be considered to have missed that assessment interval.

4. Blinding

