In CSP #591 we will offer consultation to study therapists or prescribing clinicians on best practices in medication management. [name] will perform this function by serving as the Medication Monitor, utilizing his experience providing similar consultation through VA's National PTSD Consultation Program. The goal is not to prevent clinicians from doing what they feel is in the best interests of participants, but rather, to standardize insofar as possible the use of medications across participants and sites and discourage ineffective or potentially harmful prescribing practices. We will use a blinded consult request form (modeled after the form currently used in the PTSD Consultation Program) so that [name] can remain blind to a participant's assigned treatment condition during these consults. Clinicians also will be reminded to not discuss participants' treatment assignment with [name] during any discussions that follow.

C. Discontinuation of Study Treatment

Experience with PE and CPT in the rollouts indicates that some participants will have temporary disruptions of study treatment due to other comorbid problems or life events, but that participants typically can come back into treatment after being stabilized. However, participants will be discontinued from treatment if they show substantial worsening of PTSD, other symptoms, or functioning requiring lengthy hospitalization of if the worsening is due to treatment. For intent-to-treat purposes, all participants, including those who are terminated from treatment early, will be followed at posttreatment and at 3 and 6 months.

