Treatment Session 1	0-30 days after randomization
Treatment Session 2-14*	7-21 days after previous session
Mid-Treatment Assessment (Session 6)	0-14 days after session 6
Post Treatment Assessment	0-14 days after final treatment session
3-month Assessment	3 months ±2 weeks after final treatment session
6-month Assessment	6 months ±2 weeks after final treatment session

* The site SC and therapist will make sure Treatment Session 7 is scheduled after the "Mid-Treatment Assessment (session 6)" visit.

K. Rules for handling windows with more than one visit

Visit follows sequentially from previous visit. Thus, it won't be an issue for this study. If a visit is late in the follow-up phase, the late visit will be assigned to the visit with the closest target date.

L. Data inclusion/exclusion decision rules

Plan to use the data from all randomized participants in the analyses, regardless of the number of sessions they have completed. However, for sites with questionable data the study Executive Committee and Data Monitoring Committee will make recommendation to CSR&D Director whether to exclude the data from analyses or not.

M. Definition of compliance

Treatment compliance and termination will be reported and monitored. Regardless of their treatment compliance levels, the data from all participants will be used for analyses.

N. Methods for handling multiple observations

Appropriate methods for analyzing repeated measures data (e.g., mixed effects models, generalized estimating equations) as described in Sections II.H.2 and II.H.3 above.

- O. Use of baseline variables See Section II.H.1 above.
- P. Rules for calculation of derived variables See Section II.H.2 above.
- Q. Use of covariate data See Sections II.H.4 and II.H.5 above.
- R. Rules for stopping the trial, and allowance for them in the analysis See Section II.D.2 above.

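### Protocol IV.C.3 applies a screening-style contact rule to people already randomised, and would probably end their outcome follow-up contrary to the protocol's own follow-up rules

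*Protocol*

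**What the plan says.** Protocol IV.C.3 (Phase 3 screening) sets this order:

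- Assignment comes first: "Participants meeting eligibility criteria will then be assigned to treatment".
- The call follows: "The Site Coordinator will contact the participant by phone to provide information about the participant's treatment assignment and schedule the participant's initial therapy appointment".
- Then the contact rule: "The SC will attempt to contact the participant by phone 5 times and finally with a letter requesting a response of interest in the study".
- Then the disposition: "If there is stil no response it will be assumed that the potential participant is no longer interested in the study".

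Table II.1 and VI.A give the same order: randomisation is done and recorded before the first session is scheduled. The Appendix E entry for version 1.3 also describes this text as the procedure for telling participants their assignment and booking the first appointment.

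The follow-up rules elsewhere are broader. VIII.C says that "all participants, including those who are terminated from treatment early, will be followed at posttreatment and at 3 and 6 months", for intention-to-treat purposes. X.F promises attempts at every timepoint whatever happens to treatment. VIII.A.3 has its own limit, "Five contact attempts including a final letter will be made before a participant is considered to be" unreachable, and confines that status to the timepoint in question. VIII.D ends follow-up for those who withdraw consent. It also recognises a lost-to-follow-up status, from which a person may be re-consented.

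On analysis, SAP II.L states: "Plan to use the data from all randomized participants in the analyses, regardless of the number of sessions they have completed". Protocol X.D.2 analyses by randomised group however many sessions were attended.

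**The concern.** The wording belongs to screening. IV.C.1 has almost the same rule for people who have not yet consented: "The SC will contact the potential participants initially by phone (up to 5 times) and then by mail with a letter". There, silence can fairly close the file. In IV.C.3 the person is a randomised participant, and one round of silence is read as loss of interest in the study as a whole, not only in therapy.

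No other text gives sites a workable instruction for someone who never starts. The SAP II.J windows for the post-treatment, 3-month and 6-month assessments all count from the last therapy session, which a non-starter does not have. A coordinator would naturally follow IV.C.3 and make no further contact.

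At stake is avoidable loss of the primary outcome. Non-starters plausibly improve less than treated participants. If they leave only a baseline CAPS, the mixed model, under missing at random, in effect gives them the mean change of their arm. The coordinator making the calls knows the assignment, so contact effort, and with it the loss, could differ by arm.

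**Working it through.** **1. The plan's sample size, as a reference.** Inputs from protocol X.B.2-3: therapist variance 36, within-subject variance 174, t = 3 post-treatment scores, m = 8 participants per therapist, target difference 5, two-sided alpha 0.05, power 90%.

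- tau² = 36 + 174/3 + 174 = 268, so tau = 16.37.
- rho = 36/268 = 0.134, and f = 1 + 7 × 0.134 = 1.94.
- n per group before inflation = 2 × (1.960 + 1.282)² × 268/25 = 225.3.
- After inflation: 225.3 × 1.94 = 437.1, rounded up to 438 per group, total 876. The plan has 878; rounding to 226 before inflating gives 226 × 1.94 = 438.4, hence 439 per group.

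The figure reproduces. It does not depend on the contact rule.

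**2. Power if never-reached participants give no post-baseline CAPS.** The documents give no share, so the shares below are assumptions. Power uses 450 × (1 − share) per group divided by the design effect, with t = 3 for everyone else.

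| Assumed share never reached | Participants of 900 | Power, caseload held at 8 | Power, caseload falls in proportion |
|---|---|---|---|
| 0% | 0 | 90.8% | 90.8% |
| 5% | 45 | 89.4% | 90.2% |
| 10% | 90 | 87.7% | 89.4% |
| 15% | 135 | 85.8% | 88.6% |

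**3. Bias in the PE-CPT contrast.** Let p be the share of an arm lost in this way and D the amount by which their true mean change falls short of that of the treated. Giving them the arm mean overstates that arm's improvement by p × D, so

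bias = p_PE × D_PE − p_CPT × D_CPT.

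Assumptions, none from the documents: p_PE 5-10%, p_CPT 2-5%, common D of 10-20 points.

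- Lowest: (0.05 − 0.05) × D = 0.
- 5% v 2%: 0.03 × 10 = 0.3 to 0.03 × 20 = 0.6.
- 10% v 5%: 0.05 × 10 = 0.5 to 0.05 × 20 = 1.0.
- Highest: (0.10 − 0.02) × 20 = 1.6, which is 1.6/5 = 32% of the target difference.

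Equal loss gives zero bias only if D is also equal in the two arms.

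**4. The part due to this rule.** Had attempts continued, only some of these people would have answered an assessor. If that fraction is r in both arms and those people have the same D, the avoidable bias is r times the figure above. For illustration, r = 0.5 turns the top value into 0.5 × 1.6 = 0.8 points. The documents give no value for r.

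**The case against.** The strongest reply is that the sentence excludes nobody. A reader might infer a post-randomisation exclusion from the intention-to-treat population. The documents do not support that: IV.C.3 speaks of interest and is silent on analysis, while X.D.2 and SAP II.L keep every randomised participant. The model in X.B.1 treats baseline as one of its timepoints, so a baseline-only participant can stay in it.

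A reader might also infer heavier loss in PE, because I.C.3 reports a decision-aid trial in which 34% wanted CPT and 3.8% PE. That is weak support. Someone never reached has not heard the assignment from these calls. In the same trial 43.9% had no preference. Another cited study found 50% preferring PE, although cognitive therapy was not offered there, and I.C.2 cites no difference in dropout between therapy types. Randomised participants have also agreed to either treatment.

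Three further points carry some weight. VIII.D and Appendix B Table B.8 already recognise loss to follow-up, and VIII.D gives a way back through re-consent. Many people who ignore five calls and a letter would also not answer assessors. Multiple imputation is planned, as are analyses under non-ignorable missingness when large fractions of information are missing (X.F, SAP II.S).

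These limit the size of the problem but do not remove it. Declaring a participant lost before the first follow-up assessment is due is the step in dispute. With only a baseline score, linear interpolation is impossible and completer analyses leave the person out. A loss of a few per cent may not trigger the non-ignorable analyses.

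**Conclusion.** The conflict is real and worth correcting. IV.C.3 acts after randomisation, uses a term for people not yet enrolled, and infers loss of interest in the study from one round of silence. VIII.C, X.F and VIII.A.3 require continued attempts. The likely result is an avoidable stop in follow-up and missing primary outcomes, not a stated exclusion from the analysis.

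The size is uncertain and probably modest. The power loss is small over plausible shares. The bias range of 0 to 1.6 points rests wholly on assumed loss rates and an assumed change deficit, and only the recoverable fraction can be charged to this rule. The documents give no basis for saying which arm would lose more.

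**What to change.** - **Protocol IV.C.3:** replace the last sentence. A randomised participant who does not respond is recorded as randomised, did not start study treatment, and stays in the study. Contact for the post-treatment, 3-month and 6-month CAPS proceeds under VIII.A.3, with failed contact counted as a miss at that timepoint only. Attempts end early only on withdrawal of consent. State that the lost-to-follow-up status in VIII.D is not assigned from this single round of calls.
- **SAP II.J:** for non-starters, anchor the three assessment windows to a date such as randomisation plus the standard treatment duration (Table II.1 shows treatment ending at week 12). Without this, the protocol change has no dates to work from.
- **SAP analysis text:** report non-starters by arm, and say how the therapist random effect is coded for a participant with post-baseline scores but no therapist.

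Cost: a short amendment to both documents and some extra telephone attempts by assessors already in place. The sample size is unaffected.
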